## List of Abbreviations and Definition of Terms

Abbreviation	Definition
ADP	Adenosine diphosphate
AE	Adverse event
ALT	Alanine aminotransferase
ASA	Acetylsalicylic acid
AST	Aspartate aminotransferase
ATC	Anatomical therapeutic chemical
BT	(Skin) Bleeding time
BMI	Body mass index
CI	Confidence interval
CYP	Cytochrome P450
ECG	Electrocardiogram
EudraCT	European Clinical Trial Data Base
FAS	Full analysis set
IMP	Investigational medicinal product
IPA	Inhibition of platelet aggregation
MedDRA	Medical Dictionary for Regulatory Activities
OPC	Otsuka Pharmaceutical Co.
PE	Physical examination
PRP	Platelet rich plasma
SAP	Statistical analysis plan
TEAE	Treatment-emergent adverse event
VASP	Vasodilator-stimulated phosphoprotein
WHO-DD	World Health Organization Drug Dictionary

## 1 Introduction

This statistical analysis plan (SAP) documents the statistical analysis methodology and data analysis algorithms and conventions to be applied for a statistical analysis and reporting of pharmacodynamic and safety data of Trial 21-13-102. All amendments to the protocol are taken into consideration in developing the SAP.

## 2 Trial Objectives

The primary objective of this trial is to determine the effects of orally administered cilostazol 100 mg twice daily, Acetylsalicylic acid (ASA) 100 mg once daily or clopidogrel 75 mg once daily alone as well as in combination of cilostazol 100 mg twice daily/ clopidogrel 75 mg once daily or cilostazol 100 mg twice daily/ ASA 100 mg once daily on ex-vivo platelet function testing.

A key secondary objective is the effect of orally administered cilostazol 100 mg twice daily, ASA 100 mg once daily or clopidogrel 75 mg once daily alone as well as in combination of Cilostazol 100 mg twice daily/ clopidogrel 75 mg once daily or cilostazol 100 mg twice daily/ ASA 100 mg once daily on bleeding time in healthy subjects. While bleeding time is an important parameter in this regard it also does exhibit a higher level of intra- as well as interindividual variability and an additional tissue dependent variability. Therefore, bleeding time is evaluated as a key secondary parameter.

In addition, the effects of a combined administration of cilostazol 100 mg twice daily/ clopidogrel 75 mg once daily in subjects with a homozygous wildtype allele of *CYP2C19* (\*1/\*1) showing normal *CYP2C19* activity will be compared with the effects of subjects carrying either the heterozygous *CYP2C19* (\*1/\*2) isoform and with subjects carrying the homozygous *CYP2C19* (\*2/\*2) isoforms, displaying a intermediate and poor *CYP2C19* activity, respectively.

A further secondary objective is to assess the safety variables after the orally administration of cilostazol 100 mg twice daily, ASA 100 mg once daily or clopidogrel 75 mg once daily alone as well as a combination of cilostazol 100 mg twice daily/ clopidogrel 75 mg once daily or cilostazol 100 mg twice daily/ ASA 100 mg once daily.

[figure not shown]

### 3 Trial Design

#### 3.1 Type/Design of Trial

An open-label, single center, parallel group trial in healthy volunteers.

The trial will be conducted at one (1) investigational site in Germany.

**Figure 3.1-1 Trial Design Schematic**

### 3.2 Trial Treatments

After signing screening informed consent, approximately 2000 subjects will be screened to evaluate inclusion/ exclusion criteria and to determine subjects *CYP2C19* genotype.

Screening will be performed until:

at least 38 (34+ 4 = replacements) subjects with *CYP2C19* *wildtype allele* (\*1/\*1) (normal *CYP2C19* activity)

and

at least 19 (17+2 = replacements) subjects with *CYP2C19* *heterozygous* (\*1/\*2) isoform (intermediate *CYP2C19* activity)

and

at least 19 (17+2 = replacements) subjects with *CYP2C19* *homozygous* (\*2/\*2) isoform (poor *CYP2C19* activity) have been identified and screened.

For the purpose of statistical analyses 34 evaluable subjects with normal *CYP2C19* activity, 17 evaluable subjects with intermediate *CYP2C19* activity, and 17 evaluable subjects with low *CYP2C19* activity are required. Subjects who are considered not evaluable after the start of the trial (eg, due to early termination, or protocol violation) will be replaced. Any replacement subjects must begin the trial at the start of the protocol.

The stated number of replacements for the individual study groups are estimates and may become higher in the case that data of unexpectedly high numbers of subjects are found to be of not evaluable in the course of the study.

All subjects suitable for enrolment/randomization are required to meet all inclusion criteria and no exclusion criterion.

The *CYP2C19* genotype will be determined by commercially-available technology. The Spartan RX® System will be used, allowing determination of the *CYP2C19* phenotype within 60 minutes in the patient's saliva. The assay allows to discriminate between the *CYP2C19* *wildtype allele* (\*1/\*1, normal *CYP2C19* activity), *heterozygous* (\*1/\*2, low *CYP2C19* activity) and *homozygous* (\*2/\*2, low *CYP2C19* activity) alleles.

The assay directly detects the *CYP2C19*\*2, \*3, and \*17 alleles. Besides the \*1 allele these are the alleles with the highest frequency in Caucasian populations. The system

reports for each allele whether none, one or two copies of it are detected. Detection of one or two \*2 alleles, for example, allows to determine whether the test subject has a *CYP2C19*\*1/\*2 or *CYP2C19*\*2/\*2 genotype. If no copy of the \*2, \*3 or \*17 alleles is detected it can be concluded that the test subject has a \*1/\*1 genotype.

The Spartan RX® *CYP2C19* system is certified in Europe and the testing will be performed by trained investigational site staff.

After signing treatment informed consent, 68 subjects will undergo further screening procedures in order to determine baseline characteristics. Subjects failing these procedures will be replaced by screened subjects matching the genotype (normal, intermediate or poor *CYP2C19* activity).

All 68 subjects will then be included in the treatment phase of the trial and will receive during the first week cilostazol 100 mg twice daily for 1 week (trial period A), followed by a 1 week wash-out period (trial period B, return to baseline). Subjects who fail to return to baseline with respect to platelet function testing and skin bleeding time will be re-tested within a further week.

Subjects will be stratified and randomized into 4 treatment groups according to their *CYP2C19* genotype (normal or low *CYP2C19* activity).

- Treatment group 1 will consist of subjects with *CYP2C19* wildtype allele (\*1/\*1) and will receive standard doses of ASA 100 mg/day (Group 1, n=17) for 1 week (trial period C).
- Treatment group 2 will consist of subjects with *CYP2C19* wildtype allele (\*1/\*1) and will receive standard doses of clopidogrel 75 mg/day (Group 2, n=17) for 1 week (trial period C).
- Treatment group 3 will consist of subjects with *CYP2C19* heterozygous (\*1/\*2) isoform and will receive standard doses of clopidogrel 75 mg/day (Group 3, n=17) for 1 week (trial period C).
- Treatment group 4 will consist of subjects with *CYP2C19* homozygous (\*2/\*2) isoform and will receive standard doses of clopidogrel 75 mg/day (Group 3, n=17) for 1 week (trial period C).

In the following week subjects in all treatment groups will receive cilostazol 100 mg twice daily for 1 week on top as an add-on therapy (trial period D).

Drug intake of ASA and clopidogrel will be in the morning hours, for cilostazol drug intake will be twice daily: once in the morning and once in the evening.

### **3.3 Trial Population**

#### **3.3.1 Number of Subjects and Description of Population**

Approximately 2000 subjects will be screened and their *CYP2C19* genotype will be determined in order to identify at least 17 + 2 subjects with *CYP2C19 heterozygous* (\*1/\*2) isoform (Group 3) and 17 + 2 subjects with *CYP2C19 homozygous* (\*2/\*2) isoforms (Group 4) and at least 34 + 4 subjects with *CYP2C19 wildtype allele* (\*1/\*1) (Group 1+2).

This number of approximately 2000 subjects in screening is based on the published ~30% prevalence of *CYP2C19 heterozygous* (\*1/\*2) and 2% to 5% of *CYP2C19 homozygous* (\*2/\*2) isoforms in the Caucasian population and under consideration of the fact that the \*2 isoform is closer to the lower end of probability in the German population.

A total of 68 healthy male volunteers, aged 18 to 45 years, will be dosed with trial medication and complete all trial procedures and periods. Trial participants who will early terminate their trial participation will be replaced. If the scheduled evaluation of the primary efficacy parameter (outlined in Section 6.1) cannot be performed (e.g. for technical reasons), additional subjects may be enrolled at the sponsor's discretion in agreement with the principal investigator. Any replacement subjects must begin the trial at the start of the protocol.

#### **3.3.2 Subject Selection and Numbering**

The investigational site will identify potential trial participants and perform screening procedures. Screened subjects will be assigned a unique identification number. The investigational site will maintain a confidential list identifying all subjects.

### **3.4 Trial Visit Window**

Nominal visit will be used as analysis visit for analyses. The data from unscheduled visits will be not included in the summary tables.

## **4 Sample Size**

The primary variable of the trial is ex-vivo inhibition of platelet aggregation. Comparisons of the inhibition of platelet aggregation are made between subjects during treatment of reference medication alone (Reference) and during the concomitant treatment of reference medication and cilostazol (Test). When assuming that the expected platelet aggregation treatment mean ratio is 1 with a standard deviation of 27% (Angiolillo *et al*, 2011) , for showing equivalence of a single parameter, a sample size of 17 patients per group would be required to provide a 90% power. That is, with the crossover design, 17 subjects yield a probability of 0.95 to reject the null hypotheses that the platelet aggregation with treatment of cilostazol along with reference medication versus reference medication alone is below 0.70 or above 1.43, ie, the 95% confidence interval (CI) is contained within the equivalence limit [0.70,1.43].

Ex-vivo inhibition of platelet aggregation is the primary endpoint of the study and accordingly study hypothesis and sample size estimation has been based on the primary endpoint. Similar considerations apply to the assessment of bleeding time, for which the biological variation is considered to be greater than for platelet aggregation, as it is affected additionally by tissue- or organ-dependent differences in the physiology of the vascular bed. The hypothesis tested for bleeding time will be analogue to these tested for platelet aggregation, however, the statistical power of treatment effects estimated for platelet aggregation does not apply to bleeding time.

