## **11 Pharmacodynamic Analyses**

### **11.1 Statistical Analyses of Primary Pharmacodynamic Endpoints**

#### **11.1.1 Inhibition of Platelet Aggregation**

- 1) Equivalence will be indicated if the 95% confidence interval (CI) for the ratio (Test/Reference) of the IPA is contained within the equivalence limits of 0.70 to 1.43 for each parameter of platelet aggregation.

Primary Analysis will be performed on the natural-log transformed IPA. The mixed-effect linear model for each parameter will include a term for treatment regimen as a fixed effect, and a term for subject as a random effect. From each analysis, the least squares treatment means and difference (T - R) and the 95% CI for the treatment difference will be obtained. Then, the antilogs of the difference and the confidence limits will provide the estimate and 95% CI for the ratio (T/R) of the geometric means of platelet aggregation parameters of the test and reference.

This method will be used to compare drugs/combinations, ie, cilostazol/clopidogrel vs clopidogrel alone; cilostazol/ASA vs ASA alone, as well as the different genotype combinations.

For the not log-transformed data, the same analyses will be conducted exploratory.

- 2) The IPA of each treatment regimen will be summarized using the descriptive statistics. The means for the treatment difference (T-R) and their 95 % CI will be calculated.

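### The primary Test/Reference contrast is a fixed-sequence add-on comparison, not the crossover named in SAP Section 4, so T/R includes any change from Period C to Period D and the stated 0.95 does not hold

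*SAP*

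**What the plan says.** The SAP describes the design in several places, and the descriptions differ.

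- **Section 3.1:** "An open-label, single center, parallel group trial in healthy volunteers".
- **Section 4:** "That is, with the crossover design, 17 subjects yield a probability of 0.95 to reject the null hypotheses". Earlier in the same paragraph the Test and Reference comparison is described as made between subjects, and the power is given as 90%.
- **Section 3.2:** each group first takes ASA or clopidogrel alone for one week (Period C). Then: "In the following week subjects in all treatment groups will receive cilostazol 100 mg twice daily for 1 week on top" (Period D).
- **Section 3.2, on allocation:** "Subjects will be stratified and randomized into 4 treatment groups according to their" genotype. What is allocated is the treatment group. No order of Test and Reference is allocated.
- **Section 9.2:** the adverse event windows follow the same order. Reference alone runs from the start of Period C to the start of Period D, and the combination runs from the start of Period D.
- **Section 11.1.1:** the primary model on log IPA will "include a term for treatment regimen as a fixed effect, and a term for subject as a random effect". It has no period or sequence term.

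**The concern.** In a crossover, different subjects receive the treatments in different orders, so a change over time can be separated from the treatment effect. Here Test always follows Reference in the same subject, with no washout between them. Test is also measured after a second week of the reference drug, and Reference after only one. The ratio planned as the primary result is thus the effect of adding cilostazol multiplied by whatever else changed between the two weeks.

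Two things are at stake. The first is what an equivalence conclusion may be said to show. A shift between weeks could push the ratio out of the limits when cilostazol does nothing, or pull it inside them when cilostazol does something. The second is the probability in Section 4, which is tied to a design that the trial does not have.

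**Working it through.** **1. Inputs (SAP Section 4).** Expected ratio 1; standard deviation 27%; 17 subjects per group; 95% CI (0.025 per side); limits 0.70 to 1.43. On the log scale the limits are ln 0.70 = −0.3567 and ln 1.43 = 0.3577.

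*Assumption:* 27% is the within-subject variation, which the SAP does not say. Read as a CV, the log SD is √ln(1 + 0.27²) = 0.2653. Read directly as a log SD, it is 0.27. Both readings are carried through.

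**2. Method.** The standard error of the log ratio is SD × √(2/17) = SD × 0.3430, which is 0.0910 or 0.0926. Equivalence is concluded if the estimate ± t(0.975, df) × estimated SE lies inside the limits. Power is this probability, integrated over the chi-square distribution of the variance estimate.

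**3. The plan's own figure, n = 17, true ratio 1.**

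| Analysis | df | CV 27% | log SD 0.27 |
|---|---|---|---|
| 2×2 crossover, 95% CI | 15 | 0.912 | 0.899 |
| Paired, fixed sequence, 95% CI | 16 | 0.915 | 0.902 |
| 2×2 crossover, 90% CI | 15 | 0.964 | 0.958 |
| Paired, fixed sequence, 90% CI | 16 | 0.965 | 0.959 |

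The 90% power reproduces. The 0.95 does not reproduce with the stated 95% CI: the paired design needs 19 subjects (CV 27%) or 20 (log SD 0.27) to reach it. With 17 subjects, 0.95 is reached only with a 90% CI.

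If 27% were instead the SD of the paired log difference, power would be 0.998 to 0.999 and 10 subjects would suffice for 90%. That reading does not explain the choice of 17.

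**4. Why a period effect cannot be estimated.** For subject *i* in any group, let τ be the log effect of adding cilostazol and π any log change from Period C to Period D.

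- Period C (Reference): log IPA = μ + subject*ᵢ* + error
- Period D (Test): log IPA = μ + subject*ᵢ* + τ + π + error

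The mean difference estimates τ + π, so the back-transformed ratio estimates exp(τ) × exp(π). No subject takes Test in Period C or stays on Reference alone in Period D. The data therefore hold nothing that separates τ from π, and adding a period term would not help.

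**5. What a shift would do.** The SAP gives no value for π, so these sizes are illustrations (n = 17, df 16, 95% CI).

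| True cilostazol ratio | Shift C to D | Ratio estimated | P(equivalence), CV 27% | log SD 0.27 |
|---|---|---|---|---|
| 1 | none | 1.00 | 0.915 | 0.902 |
| 1 | +5% | 1.05 | 0.876 | 0.863 |
| 1 | +10% | 1.10 | 0.769 | 0.753 |
| 1 | −10% | 0.90 | 0.734 | 0.719 |
| 1 | +20% | 1.20 | 0.441 | 0.428 |
| 1.43 | none | 1.43 | 0.025 | 0.025 |
| 1.43 | −10% | 1.43 × 0.9 = 1.287 | 0.192 | 0.187 |

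**The case against.** The strongest reply is that the labels do little harm. Four groups do run in parallel, and Test and Reference are compared within subject, so each label loosely fits one layer of the design. Section 3.2 states the fixed order openly. Moving from crossover to paired degrees of freedom changes power by only 0.003, and the model suits the data that will exist. All of this stands. It means that the sample size and the model are not at fault, and that no redesign is called for.

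A reader might infer that the SAP claims control of period effects. It does not: it uses the word crossover, but nowhere asserts balanced order or control of time effects.

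A reader might also infer that the primary result is biased by the amounts tabulated above. The document does not support that either, since it gives no drift figure. Upward shifts also have a ceiling. If aggregation is not negative, IPA cannot exceed 100%. A ratio of 1.20 is then out of reach for a subject whose Reference IPA is above 100/1.20 = 83%, and a ratio of 1.43 above 100/1.43 = 70%. The SAP gives no IPA levels, so which scenarios are possible in which group is unknown.

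It could also be said that a limitation of this kind belongs in the protocol or the report. The protocol is not at hand and may carry it. But the SAP itself puts the word crossover and the figure 0.95 in one sentence, and that sentence needs correcting wherever the limitation is recorded.

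**Conclusion.** The concern holds as a matter of design description, stated power and interpretation. The primary contrast is a fixed-sequence, within-subject add-on comparison inside four parallel groups. Regimen is fully aliased with period, so T/R includes any week-1 to week-2 change in the reference effect or the assay, in either direction, and the planned model cannot show it. Whether such a change exists, and how large it is, is unknown.

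Seventeen subjects per group remain adequate for 90% power, on the assumption that 27% is within-subject. The probability for the paired contrast is about 0.90 to 0.915, where Section 4 says 0.95.

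**What to change.** 1. **Sections 3.1 and 4:** describe the trial as a fixed-sequence within-subject comparison (Period C, then Period D) within four parallel groups. For the primary contrast, delete the word crossover and the description of the comparison as between subjects.
2. **Section 4:** state power for a paired contrast with n − 1 degrees of freedom: about 0.90 to 0.915 for n = 17 with a 95% CI, in place of 0.95. Say that 27% is taken as the within-subject SD or CV. N does not change.
3. **Section 11.1.1:** state that T/R compares week-2 reference plus cilostazol with week-1 reference, and that attributing it to cilostazol assumes no period or duration effect.

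A drift check that compares drug-free aggregation at the end of Period B with Visit 1 may look attractive, but it should be left out or reported only as descriptive. Those measurements precede any reference drug, so they do not test a week-1 to week-2 change on it. They are also on the aggregation scale while T/R is a ratio of IPA, and a null result could falsely reassure.

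The cost is a few sentences in the SAP and a slightly more cautious conclusion. No new subjects, visits or analyses are needed.

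### SAP Section 4 gives two powers, 90% and 0.95, for the same 17 subjects and the same equivalence criterion; the stated inputs support about 0.90

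*SAP*

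**What the plan says.** Section 4 (Sample Size) of the SAP assumes that "the expected platelet aggregation treatment mean ratio is 1 with a standard deviation of 27" per cent, and concludes that "a sample size of 17 patients per group would be required to provide a 90% power", for equivalence of a single parameter. The following sentence is introduced as a restatement: "with the crossover design, 17 subjects yield a probability of 0.95 to reject the null hypotheses". The null hypotheses it names are a ratio below 0.70 and a ratio above 1.43, and it ends by explaining the event as one in which "the 95% confidence interval (CI) is contained within the equivalence limit [0.70,1.43".

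Section 11.1.1 uses the same decision rule. The 95% CI for the test/reference ratio must be "contained within the equivalence limits of 0.70 to 1.43 for each parameter of platelet aggregation". The analysis is on the natural-log scale, with treatment regimen as a fixed effect and subject as a random effect, so each comparison is within subject. No other section gives a power or explains the difference between the two figures.

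**The concern.** Two consecutive sentences give different powers for one design, and the second is presented as saying the same thing as the first. The second cannot be read as describing a different event, because its closing clause ties 0.95 to the whole CI lying inside the limits, which is the overall equivalence criterion.

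The complement of the power is the chance of failing to show equivalence when the treatments are truly equivalent. At 0.95 that chance is 5%; at 0.90 it is 10%, twice as large. A reader interpreting a failed equivalence test cannot tell which applies. Nor can the reader settle it by recalculation without guessing, because the SAP does not say whether the 27% is a within-subject SD, a CV or the SD of the paired difference.

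**Working it through.** **Inputs**

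- n = 17 per group, true ratio 1, variability 27% (SAP Section 4).
- Limits 0.70 and 1.43, with a 95% CI (Sections 4 and 11.1.1). This amounts to two one-sided tests at 0.025 each.
- Log scale, paired comparison (Section 11.1.1).
- Assumption: 27% is within-subject, taken either as a log-scale SD, σ = 0.27, or as a CV, σ = √ln(1 + 0.27²) = 0.265.
- Degrees of freedom: n − 1 = 16, or n − 2 = 15 as a variant.

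**Set-up**

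- Log limits: ln 0.70 = −0.3567 and ln 1.43 = 0.3577.
- Standard error of the mean log difference: SE = σ√(2/n). For σ = 0.27 this is 0.27 × √(2/17) = 0.0926; for σ = 0.265 it is 0.0910.
- Critical value: t(0.975, 16) = 2.120, or t(0.975, 15) = 2.131.
- With d the mean log difference and ŝ its estimated standard error, power = P(d − t·ŝ > ln 0.70 and d + t·ŝ < ln 1.43). It is obtained by integrating the normal probability for d over the chi-square distribution of the estimated variance.

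**The plan's 90% figure, and the n needed for 0.95**

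| n | σ = 0.27, df n−1 | σ = 0.27, df n−2 | CV 27%, df n−1 | CV 27%, df n−2 |
|---|---|---|---|---|
| 16 | 0.875 | 0.870 | 0.889 | 0.885 |
| 17 | 0.902 | 0.899 | 0.915 | 0.912 |
| 19 | 0.941 | 0.940 | 0.950 | 0.948 |
| 20 | 0.955 | 0.954 | 0.962 | 0.961 |

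A simulation of 400,000 trials for CV 27% with 16 df also gives 0.915. The claim of 17 for 90% is reproduced: 17 is the smallest n reaching 0.90 in three of the four variants. In the fourth (σ = 0.27, n − 2 df) n = 17 gives 0.899 and 18 would be needed.

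For 0.95, the smallest n is 19 for CV 27% with n − 1 df, and 20 in the other three variants.

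**SD that each stated power would require at n = 17 (16 df)**

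- For 0.90: log-SD 0.271 (CV 27.6%), which fits the stated 27%.
- For 0.95: log-SD 0.249 (CV 25.3%), which does not.

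**Other ways to reach about 0.95 at n = 17**

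| Reading | Power (σ = 0.27 / CV 27%) |
|---|---|
| One of the two one-sided tests alone, 16 df | 0.951–0.952 / 0.957–0.958 |
| Normal approximation, both tests | 0.942 / 0.951 |
| 90% CI instead of 95%, 16 df | 0.959 / 0.965 |
| 27% as SD of the paired log difference, 16 df | 0.998 / 0.999 |

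The first row is not the CI-containment event that the sentence describes. The second uses a method the SAP does not mention, and it still conflicts with the 90%. The third contradicts the 95% CI in both sections. The fourth matches neither stated figure.

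**Risk of missing equivalence at a true ratio of 1**

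From 1 − 0.915 = 0.085 to 1 − 0.899 = 0.101, so about 9 to 10% per parameter and group, against the 1 − 0.95 = 5% implied by the second sentence.

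**The case against.** The strongest defence is that both numbers are correct but describe different things. With a log-SD of 0.27, each one-sided test at 0.025 has power of about 0.95, and the chance that both reject is about 1 − 2 × 0.05 = 0.90. The sentence speaks of null hypotheses in the plural, so the author may have had per-test power in mind. This may well be how the figure arose, and the SAP cannot settle it. It does not rescue the text. Nothing labels 0.95 as a per-test power, and the closing clause attaches it to the whole CI lying within the limits, which requires both rejections.

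A second objection concerns consequence. The Section 4 assumption is worded for platelet aggregation, whereas Section 11.1.1 says "Primary Analysis will be performed on the natural-log transformed IPA", where IPA is a percentage change from baseline. The SAP gives no SD for log IPA, so neither 0.90 nor 0.95 is shown to be the power of the primary test. That stands as a limit: the recalculation checks Section 4 on its own inputs and no more.

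Third, Section 14 describes drop-outs in the past tense, so a correction could not alter enrolment. That also stands. The correction affects what is reported and how a failed test is read, and the wrong figure should still not be carried forward.

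Finally, Section 4 already says that the power is for a single parameter, per group, at a ratio of 1. Only the nature and scale of the 27% are truly missing.

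**Conclusion.** The concern holds. The contradiction between 90% and 0.95 is plain from the text and needs no calculation. On the stated inputs the overall power is 0.899 to 0.915, so the 90% sentence is sound and 0.95 is about 3.5 to 5 percentage points too high. These recomputed values assume that the 27% is a within-subject log-scale SD or CV. Of the log-scale readings tried, only this one yields 17 subjects for 90% power with a 95% CI. The sample size and the decision rule are not affected.

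**What to change.** In SAP Section 4:

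1. Replace the probability of 0.95 with 0.90. If the per-test figure is to be kept, label it as the power of each one-sided test and give 0.90 as the probability that the whole 95% CI lies within 0.70 to 1.43.
2. State that the 27% is a within-subject value, if that is what was used, and whether it is a log-scale SD or a CV.
3. Keep the qualification that the power is for a single parameter, per group, at a true ratio of 1, and attach it to the corrected figure.

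If 0.95 was really the intended overall power, the SAP should say that 17 falls short of it, since 19 to 20 subjects would be needed on these inputs.

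The cost is a wording change in one section. The sample size of 17, the margin, the CI level and the model stay as they are.
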